### 3.2 Trial Treatments

During the double-blind treatment phase, subjects will receive IMP consisting of brexpiprazole monotherapy or placebo, depending on the subject's treatment assignment.

As shown in [Table 3.2-1](#), subjects will receive a starting dose of 2 mg/day of brexpiprazole (or corresponding placebo) from Days 1 to 3, followed by titration to 3 mg/day brexpiprazole (or placebo) on Day 4. Subjects may be titrated (or re-titrated) to a higher dose of brexpiprazole (or placebo), up to a maximum of 4 mg/day, based on treatment response and at the investigator's discretion anytime at Day 7 or thereafter. Subjects who are unable to tolerate their current dose can be titrated down at any time to a minimum of 2 mg/day. Dose adjustments must be made in increments of 1 mg/day. Subjects who are unable to tolerate 2 mg/day brexpiprazole will be discontinued from the trial.

Table 3.2-1 Dosing Schedule			
Dose	Days 1-3	Days 4a	Days 7-21b
Brexipiprazole	2 mg	3 mg	2-4 mg
Placebo	Placebo	Placebo	Placebo

aDown titration can occur at any time due to tolerability after Day 4. The minimum dose allowed is 2 mg/day.

bOption to titrate 2 to 4 mg (i.e., 2 mg, 3 mg, or 4 mg) based on clinical response and tolerability; changes must occur in 1 mg/day increments. Increases up to 4 mg/day may occur no earlier than Day 7.

All doses of IMP should be taken at the same time each day, if possible, and can be taken without regard to meals. If tolerability issues arise, the timing of administration of the IMP may be adjusted at the investigator's discretion in order to achieve optimum tolerability and compliance. Subjects will be counseled on the importance of taking the IMP.

### 4 Sample Size and Power Justification

It is anticipated that approximately 320 subjects will be randomized from an estimated 45 sites in the US and Europe. The primary efficacy endpoint is the change from baseline to Day 21 in the double-blind treatment phase in the YMRS Total Score. The trial will compare the placebo arm to the brexpiprazole arm, randomized at a ratio of 1:1, with an overall significance level of 0.05 (2-sided) for the primary endpoint.

CCI

SAP 331-201-00080

CCI

The planned sample size of 304 evaluable subjects (152 in each treatment arm) will yield at least 90% power to detect the treatment effects at a 2-tailed significance level of 0.05.

A sufficient number of subjects will be enrolled and randomized to achieve approximately 304 evaluable subjects in the double-blind treatment phase CCI

the total number of subjects to be randomized is 320 (160 in each treatment arm).

In order to ensure 304 evaluable subjects, CCI

## 5 Data Sets for Analysis and Missing Data

### 5.1 Data Sets for Analysis

The following analysis samples are defined for this trial:

Enrolled Sample: comprises all subjects who signed an ICF for the trial and enrolled into the trial.

Randomized Sample: comprises all subjects who were randomized in the double-blind treatment phase. Subjects are considered randomized when they are assigned a treatment number by IWRS at the end of screening. A subject receiving IMP outside of the IWRS will not be considered randomized, but safety will be reported.

Safety Sample: comprises those randomized subjects in the double-blind treatment phase who received at least 1 dose of double-blind IMP as indicated on the dosing record. Subjects will be excluded from this population only if there is documented evidence (i.e., drug dispensed = drug returned or no IMP dispensed) that the subject did not take IMP. If a subject is dispensed IMP and is lost to follow up, he/she will be considered exposed.

CCI

SAP 331-201-00080

## 5.2 Handling of Missing Data

The YMRS is utilized as the primary efficacy assessment of a subject's level of manic symptoms. The YMRS consists of 11 items: 1) elevated mood, 2) increased motor activity-energy, 3) sexual interest, 4) sleep, 5) irritability, 6) speech (rate and amount), 7) language-thought disorder, 8) content, 9) disruptive-aggressive behavior, 10) appearance, and 11) insight. Seven items are rated on a 0- to 4-scale, while four items (Items 5, 6, 8, and 9) are rated on a 0- to 8-scale with 0, 2, 4, 6, and 8 being the possible scores (twice the weight of the other items). For all items, 0 is the "best" rating and the highest score (4 or 8) is the 'worst' rating. The YMRS Total Score is the sum of ratings for all 11 items; therefore, possible total scores range from 0 to 60. The YMRS Total Score is set to be missing if less than 9 of the 11 items are recorded. If 10 of the 11 items are available and the item missing is from items 5, 6, 8 or 9, then the YMRS Total Score is the sum of scores for items 1 to 4, 7, 10 to 11 plus the mean of the recorded items from 5, 6, 8 and 9 times four. If 10 of the 11 items are available and the item missing is from items 1 to 4, 7, 10 to 11, then the YMRS Total Score is the sum of scores for items 5, 6, 8 and 9 plus the mean of the recorded items from 1 to 4, 7, 10 to 11 times seven. If 9 of the 11 items are available and both missing items are from items 5, 6, 8 and 9, then the YMRS Total Score is set to be missing. If 9 of the 11 items are available and both missing items are from items 1 to 4, 7, 10 to 11, then the YMRS Total Score is the sum of scores for items 5, 6, 8 and 9 plus the mean of the recorded items from 1 to 4, 7, 10 to 11 times seven. If 9 of the 11 items are available and one of the missing items is from items 1 to 4, 7, 10 to 11, and one of the missing items is from items 5, 6, 8 and 9, then the YMRS Total Score is the mean of the recorded items from 5, 6, 8 and 9 times four, plus the mean of the recorded items from 1 to 4, 7, 10 to 11 times seven. All imputed scores are rounded to the first decimal place.

A large rectangular area of the page is completely blacked out, indicating that the original content has been redacted. The text 'CCI' is visible at the top left corner of this redacted area.

CCI

SAP 331-201-00080

CCI

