9.2 Data Collection

During each subject's visit to the clinic, a clinician participating in the trial will record progress notes to document all significant observations. At a minimum, these notes will contain:

- Documentation of the informed consent process, including any revised consents;
- Documentation of the investigator's decision to enroll the subject into the trial, the review of all inclusion/exclusion criteria prior to IMP administration, and confirmation of the subject's actual participation in the trial;
- The date of the visit and the corresponding Visit or Day in the trial schedule;
- General subject status remarks, including any significant medical findings. The severity, frequency, and duration of any AEs and the investigator's assessment of relationship to IMP must also be recorded;
- Any changes in concomitant medications or dosages;
- A general reference to the procedures completed;
- The signature (or initials) and date of all clinicians who made an entry in the progress notes.

In addition, any contact with the subject via telephone or other means that provides significant clinical information will also be documented in the progress notes as described above.

Source documents and source data will be captured electronically in this trial, and will meet the same fundamental elements of data quality (eg, attributable, legible, contemporaneous, original, and accurate) as paper records. These data will be collected

Protocol 331-201-00080

into a system that is fully validated. Changes to the data will be captured by an automatic audit trail.

The trial site will be given a tablet to directly record subject data and clinical observations on electronic forms. Designated trial site staff will not be given access to the system until they have been appropriately trained. Information to be originally captured and reviewed electronically shall include details of the subject visit and the protocol-required assessments performed as a part of these visits, medical history, AEs, and concomitant medications. Because this trial is using an electronic source record as the original point of data capture, there is no additional data entry step for the trial site for data collected directly into the application - rather, the electronic source record directly populates the trial database.

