Appendix 7 Young-Mania Rating Scale

What is the YMRS?

The YMRS is an 11-item scale which aims to provide a continuous measure rating the intensity of symptoms associated with mania. The YMRS was developed as an instrument to be used by clinicians. Young et al. suggested the ratings should be based on a 15-30 minute clinical interview which takes into consideration the patients' subjective report as well as the raters' observation. Young and his collaborators intended to improve upon previous scales by providing a larger number of items for increased sensitivity and better rater reliability through the use of defined anchor points.

Optimizing the YMRS for Research

To reduce sources of error associated with the YMRS, we would like you to use the attached scripted interview when administering the YMRS.

Conventions for the YMRS

- Use the extremes of the rating scale when the anchor points accurately describe the patient's condition. Zero really means the symptom is absent. The YMRS extremes are not meant to be held in reserve for the worst imaginable case. Rather, they include common manifestations of severe manic states.
- Always score in whole numbers, but note items 5, 6, 8, and 9 not only allow but also encourage scores between the defined anchor points.
- When in doubt between two ratings, assign the higher rating, or, on 0 – 8 scaled items, the middle rating.
- Be sure that you have enough time to conduct the interview properly – you may be able to complete the YMRS in 15 minutes, but interviews with symptomatic patients often require 30-45 minutes.
- Clarify the patient's understanding and usage of terms like "paranoid", "irritable", "hyper", and "sexual interest".

YMRS

DIRECTIONS

For each item below begin inquiry using the script. Ask additional questions if necessary to assign ratings. Rate each item using your judgement in addition to the patient's self report. Also, include any information obtained outside the interview (e.g., reports by family members, etc.).

The purpose of each item is to rate the severity of that abnormality in the patient. When several keys are given for a particular grade of severity, the presence of only one is required to qualify for that rating.

The keys provided are guides. One can ignore the keys if that is necessary to indicate severity, although this should be the exception rather than the rule.

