Rate degree of annoyance even in response to justifiable stressor (e.g., being caught in a traffic jam, being made to wait in line).

Were you often irritable?

Get a sense of the frequency of irritable or angry behavior.

How did you show your anger?

Inquire about the patient's response to situations in which they felt irritated, e.g., shouting, arguments, etc.

Notes: _____

0 Absent

Assign a rating of 0 if the patient denies any increased irritability in the past week and if there is no evidence of irritability in the interview.

1 2 Subjectively increased

A rating of 1 is warranted if the patient reports increased irritability during the past week, with no serious displays of anger by the patient (e.g., patient reports feeling more irritated or frustrated by traffic jams than usual; patient feels more snappy or less polite, with no overt anger expressed to others).

3**4 Irritable at times during interview; recent episodes of anger or annoyance on ward**

A rating of 4 is given if the patient either exhibits irritability during the interview or if the patient (or others) report that the patient has expressed anger towards others due to irritability (e.g., shouting at others in traffic; yelling at store clerk).

5**6 Frequently irritable during interview; short, curt throughout**

A rating of 6 is given if the patient is clearly irritable during most of the interview or if the patient (or others) report that the patient has been irritable nearly every day in the past week and has exhibited frequent displays of anger towards others.

7**8 Hostile, uncooperative; interview impossible**

A rating of 8 is assigned if the patient is extremely irritable or hostile during the interview, making completion of the interview impossible; patient is incapable of interactions with others.

Protocol 331-201-00080

6. Speech (Rate and Amount)

Have you been more talkative than usual?

Get a sense here if the patient feels more likely to speak with others, e.g., have they been more likely to strike up conversations or to make phone calls.

Did anyone complain that they couldn't get a word in?

Probe to see if others commented on patient's increased talking, e.g., others had difficulty contributing to the conversation.

Did you find it hard to stop talking once you got started?

Did the patient have a sense of difficulty controlling the rate or amount of speech?

Were there times you spoke so fast people had trouble understanding you?

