Did others comment that the patient's speech was jumbled or difficult to follow?

Notes: _____

0 No increase

A rating of 0 is given if no increased speech is reported or observed in the interview.

1

2 Feels talkative

A rating of 2 is assigned if patient feels more likely to speak with others, e.g., starts conversations with others, makes more phone calls than usual. However, a rating of 2 indicates that there are no aberrant processes in speech patterns, e.g. patient is clearly understood; others are able to contribute to the conversation.

3

4 Increased rate or amount at times, verbose at times

A rating of 4 indicates that the patient is clearly speaking at an increased rate and amount. Take your observation into account, as well as the patient's self-report.

5

6 Push; consistently increased rate and amount; difficult to interrupt

A rating of 6 is warranted if the patient feels a pressure to keep talking, e.g., others have difficulty getting a word in edgewise. Patient must make an effort to stop self from talking.

7

8 Pressured; uninterruptible continuous speech

A rating of 8 is indicated if patient's speech is pressured and impossible to interrupt. Patient is not able to control or slow down speech.

Protocol 331-201-00080

7. Language – Thought Disorder

This item probes for a range of difficulties with language and thought processes, ranging from mild distractibility to racing thoughts, flight of ideas, and incoherent communication.

Have you had more ideas than usual or any particularly good ideas?

Get a sense here if patient has been thinking more about special ideas or has had an increased number of ideas.

Was your thinking especially keen or clear over the past week?

Did you often get distracted?

Get a sense of the intensity and frequency of distraction, e.g., was the patient able to focus and concentrate on reading or work activities; was the patient able to stay on track in conversations?

Has your mind seemed to be going very fast?

Probe here for the presence of racing thoughts, e.g., a sense that one's thoughts are going so quickly that they are too difficult to hold onto.

Did you sometimes have so many ideas that you lost track of what you were saying?

Be sure to use your observation and clinical judgement here, e.g., is the patient able to stay on track to express a coherent message? Also note any abnormal speech processes, such as rhyming or repeating nonsensical phrases.

Were you getting lost in details?

0 Absent

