Did you find you were more aware of coincidences?**Did you find special significance in things that happened or the way things were arranged around you?****Did you notice things that other people missed, or have the sense that people were talking about you, or even trying to hurt you?**

Probe here for paranoia.

Did you have any thoughts that didn't make sense to other people?**Did you have any hallucinations?**

It is important to clarify use of the term hallucinations, e.g. did you see things that others couldn't see or did you hear things that others couldn't hear?

0 Normal

A rating of 0 indicates that the patient has exhibited none of the symptoms counting towards this item.

1 Questionable plans, new interests

A rating of 1 indicates that the patient has engaged in some new plans or interests of a possibly questionable nature, e.g., planned a spontaneous vacation (within budget), scheduled more social plans than usual; shopped more than usual without spending extravagantly. You must take into account the patient's typical budget and financial situation when judging monetary decisions. Impulsive purchases clearly out of line with patient's budget should be rated a 3 or higher depending on level of excessiveness.

3 4 Special project(s); hyperreligious

A rating of 4 indicates that the patient has taken on new projects or plans of a clearly questionable nature, e.g., spending impulsively and out of budget, impulsively building an addition to one's home without prior planning, etc. A rating of 4 would also be warranted for a sudden increase in religious participation, e.g., an individual who usually attends church on a weekly basis has attended every day in the past week and not due to some external stressor or crisis, i.e., a mother who attends church on a daily basis to pray for her child who has recently been hospitalized would not qualify as "hyper-religious".

5 6 Grandiose or paranoid ideas; ideas of reference

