A rating of 6 is warranted if the patient describes having special powers or abilities, e.g., being able to predict the future or being the "best in the world" at a particular talent or ability. An example might be the student who believes that the insights in his term paper will radically alter his professor's life. A rating of 6 might also be given if a patient reports finding special meaning or significance in everyday situations (e.g., seeing a particular sign on the street and "knowing" that it is pointing him towards a new career. If the patient exhibits clearly paranoid thinking, a rating of 6 is also justified. Be sure to clarify the patient's use of the term paranoid, e.g., use your judgment to ascertain evidence of true vs. imagined negative intentions of others.

7 8 Delusions; hallucinations

A rating of 8 is warranted for clearly psychotic sx, e.g., hallucinations or delusions.

Protocol 331-201-00080

9. Disruptive – Aggressive Behavior

In this item, you will probe for information related to the patient's ability to get along with others, e.g., argument; demanding or destructive behaviors.

How have you gotten along with other people? (Have you been cooperative?)

Were there times when you were loud, demanding, or sarcastic?

Have you had any confrontations with people? (What happened?)

Did you find yourself shouting, throwing things, or doing anything destructive?

0 Absent, cooperative

A rating of 0 indicates that the patient was fully cooperative in the interview and reported no incidents of disruptive or aggressive behavior in the past week.

1**2 Sarcastic; loud at times, guarded**

A rating of 2 indicates that the patient is either guarded or somewhat uncooperative during the interview, or the patient reports one or two incidents of sarcastic, loud, or uncooperative behavior during the past week. A rating higher than 2 would be given if patient exhibited this behavior frequently during the past week or if the incidents resulted in shouting or destructive behavior.

3**4 Demanding, threats on ward**

A rating of 4 is given if patient has been demanding or threatening several times in the past week, e.g., patient reports several incidents during the past week in which he lost his temper and shouted at store clerks, family members, etc.

5**6 Threatens interviewer; shouting; interview difficult**

A rating of 6 is given if the interview is difficult to complete due to the patient's threats or confrontational behavior.

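### Does listing only even scores for YMRS items 5, 6, 8 and 9, against a form that encourages odd ones, call for a change to the plan?

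*SAP*

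**What the plan says.** SAP 5.2 (Handling of Missing Data) puts the four double-weighted YMRS items on a "0- to 8-scale with 0, 2, 4, 6, and 8 being the possible scores". Protocol 7.3 and SAP 10.3.1 carry the same statement. All three then define the total as the sum of the 11 items, with pro-rating when one or two items are missing.

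The form in Protocol Appendix 7 is looser. Its conventions say that "items 5, 6, 8, and 9 not only allow but also encourage scores between the defined anchor points", always in whole numbers, and they send a rater who is in doubt on a 0-8 item to the score halfway between. The guidance for single items is uneven at the first severity step:

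- Item 5 (irritability): the anchor is printed at 2, but the sentence below it reads "A rating of 1 is warranted if the patient reports increased irritability during the past week".
- Item 8 (content): "A rating of 1 indicates that the patient has engaged in some new plans or interests of a possibly questionable nature". Out-of-budget purchases "should be rated a 3 or higher depending on level of excessiveness".
- Item 6 (speech): "A rating of 2 is assigned if patient feels more likely to speak with others".
- Item 9 (disruptive-aggressive behavior): "A rating of 2 indicates that the patient is either guarded or somewhat uncooperative during the interview".

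Protocol 3.7.2.1 describes the same four items as graded from 0 to 8 with five defined categories, and refers to Appendix 7.

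**The concern.** The YMRS total is the primary endpoint, and a score of at least 24 at screening and baseline is an entry criterion. The analysis sections call 1, 3, 5 and 7 impossible on four items, while the form invites them. Two worries follow.

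First, someone who builds edit checks or validates data from the SAP sentence could query or block valid ratings. This is not fanciful, because ratings go straight from the device into the database: "The trial site will be given a tablet to directly record subject data and clinical observations on electronic forms".

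Second, on item 5 two raters using the same form could give the same patient a 1 or a 2, depending on whether they follow the printed anchor or the sentence under it. If this were frequent and unequal between arms, it would reach the primary comparison.

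**Working it through.** **Does the stated range depend on the scoring rule?** Seven items with a maximum of 4 and four with a maximum of 8 give 7 x 4 + 4 x 8 = 60, the stated range. Each of the four items has 5 levels under the SAP sentence and 9 under the form, but the maximum is 60 under both.

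**Do the scoring rules fail on odd values?** With complete data the total is a sum. With one of items 5, 6, 8 and 9 missing, the rule takes the mean of the other three times four. With two of them missing, the total is missing. Nothing in these steps needs an even number.

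**How large is the mismatch on item 5?** Scoring 1 instead of 2 changes the total by 1 point. If item 6, 8 or 9 is missing, it changes by 1/3 x 4 = 1.33 points. A total of 24 with item 5 at 2 becomes 23 with item 5 at 1.

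**How far could the treatment comparison move?** The planning effect and SD are redacted, so the yardstick is back-calculated from 152 per arm, 90% power and two-sided 0.05:

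- Detectable standardized effect: (1.960 + 1.282) x sqrt(2/152) = 0.372.
- In points, for an assumed SD of 8 to 12: 0.372 x 8 = 2.97, and 0.372 x 12 = 4.46.

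Compare all raters using 1 with all raters using 2 at the first step of item 5:

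| Quantity | Assumption | Result |
|---|---|---|
| Shift in mean total | 20% to 40% of subjects at that step on Day 21 | 0.2 to 0.4 points |
| Shift in treatment difference | arms differ by 5 to 15 percentage points at that step | 0.05 to 0.15 points |
| Share of detectable effect | 0.05/4.46 to 0.15/2.97 | 1.1% to 5.1% |
| Added variance if half the raters use each value | f x 0.25, with f = 0.2 to 0.4 | 0.05 to 0.10, against 64 to 144 |

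The 5.1% pairs the largest assumed shift with the smallest assumed SD. The shift in the treatment difference is also the gap between two conventions, each of which gives a valid comparison. If the drug had no effect, the arms would be expected to have the same share at that step and the expected shift would be zero.

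**The case for a change.** The strongest case for acting is that the sentence is wrong about the primary instrument, that correcting it in three places costs almost nothing, and that neither document says how an odd score is handled or what range the tablet form accepts. It can be added that item 8 also directs a 1, which would double the figures above, and that a sensitivity run with every 1 set to 2 would show whether any of this matters.

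The wording conflict and the item 5 mismatch stand. The rest is weaker.

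- **Item 8.** The visible anchor and its guidance both say 1, so no mismatch can be read from the text. The number column for that item is also damaged in the text available (later steps show pairs such as 3 and 4), so its label carries little weight.
- **Recoding.** The form invites a deliberate 1 between the anchors at 0 and 2. Setting every 1 to 2 would overwrite legitimate ratings and could not tell them from ratings driven by the guidance sentence.
- **Editing the form.** Protocol Appendix 15 says the scales match the licensed versions and that the correct versions have been used since the trial began. Changing the guidance partway could create a difference between earlier and later ratings, for 1 point on one item.
- **Range checks.** The documents do not show the tablet's accepted range, but they also show no rule that rejects odd values. Protocol 3.7.2.1 already describes a 0 to 8 scale in terms that fit Appendix 7.

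**Conclusion.** This is a clerical slip, and correcting it would bring no analytical gain. The three sentences describe the anchor points as if they were the full set of scores. An analyst who receives a 3 on item 6 will add it as recorded, which is what the rules already do.

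The item 5 mismatch is genuine but is limited to 1 point of 60. On the assumed frequencies and SD it amounts to 0.05 to 0.15 points on the treatment difference. It is also shared between arms by design: treatment is double-blind and randomization is stratified by site (Protocol 3.6), and raters are trained and certified on the YMRS, with the same clinician rating a given subject where possible (Protocol 3.7.2). At the entry threshold it could move a subject across 24, but only before randomization, so it alters who is enrolled and does not bias the comparison.

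The conclusion rests on two things the documents do not show outright: that the electronic form accepts whole numbers as Appendix 7 instructs, and that scoring habits do not depend on treatment arm. Rater training may also settle item 5, though no such convention is visible. Nothing here is shown to alter the primary result.
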